4.7.3 Adverse Events

Verbatim descriptions of adverse events (AEs) will be mapped to a preferred term (PT) and system organ class (SOC) using the Medical Dictionary for Regulatory Agencies (MedDRA®). MedDRA version 19.0 or higher and related SMQ lists (see below) will be used for coding.

AEs will be graded according to the National Cancer Institute Common Terminology Criteria for Adverse Events (NCI CTCAE), Version 4.03. For AEs of varying severity, the most severe grade as documented on the eCRF will be used in the summaries.

According to the protocol, after informed consent has been obtained but prior to initiation of combination treatment on Day 1, only SAEs caused by a protocol-mandated intervention should be reported.

After initiation of combination treatment at or after the Baseline visit, all adverse events will be reported until 28 days after the last dose of study drug. After this period, the Investigator should report any SAEs that are believed to be related to prior study drug treatment.

An AE that started or worsened on the day of initiation of combination treatment through 28 days after the date a subject completed or early discontinued from combination treatment period' as per eCRF 'Study drug completion/Early Discontinuation' will be considered treatment emergent.

The analysis of AEs will focus on treatment-emergent AEs (TEAE), but all AEs will be listed. For AEs that might occur after initiation of investigational pirfenidone up to start of combination treatment or more than 28 days after the end of combination treatment a separate listing will be provided.

Classifications of seriousness, severity and causality are described in the protocol sections 5.2 and 5.3.

An overview of patient safety profile will present the number and proportion of patients experiencing

- all and related treatment-emergent adverse events (TEAE),
- all and related serious treatment-emergent adverse events (serious TEAE),
- all and related severe TEAE,
- all and related TEAE of special interest (AESI) (MedDRA Preferred term for STIAMP - 'Suspected transmission of an infectious agent via product' or SMQ: 'Drug related hepatic disorders – severe events only (SMQ)'),
- all and related gastrointestinal (GI) disorders (SOC: Gastrointestinal disorders),

**Pirfenidone and nintedanib — F. Hoffmann-La Roche Ltd
Statistical Analysis Plan MA29895, Version 2.0, final, 17 May 2017**

27

- hepatic side effects (MedDRA AEGT: Esbriet - Potential Hy's Law AEGT' see [Appendix 4](#)),
 - all and related clinical significant vascular event (as angina pectoris, myocardial infarction, transient ischaemic attack (TIA), stroke) (Defined as any AE included in the MedDRA SMQs Ischemic heart disease, Central nervous system vascular disorders, Haemorrhages, Embolic and thrombotic events),
 - all and related ischemic heart disease (MedDRA SMQ: Ischemic heart disease)
 - all and related cerebrovascular event (MedDRA SMQ: Central nervous system vascular disorders),
 - all and related bleeding event (MedDRA SMQ: Haemorrhages),
 - all and related thromboembolic event (MedDRA SMQ: Embolic and thrombotic events),
 - all and related major adverse cardiac event (MACE), (Specific terms from SMQs Arrhythmia related investigations, Signs and symptoms, Cardiac arrhythmia terms (incl bradyarrhythmias and tachyarrhythmias), Cardiac arrhythmias, Cardiac failure: Cardiac arrest, Cardiac death, Cardio-respiratory arrest, Sudden cardiac death, Sudden death, Ventricular asystole, Agonal rhythm, Sinus arrest, Pulseless electrical activity, Torsade de pointes, Ventricular fibrillation, Ventricular flutter, Ventricular tachycardia, Cardiac fibrillation, Cardiac flutter.)
 - all and related photosensitivity or rash (MedDRA Preferred terms Nodular rash, Photodermatosis, Photosensitivity reaction, Pruritus, Pruritus generalized, Rash, Rash erythematous, Rash generalized, Rash macular, Rash maculo-papular, Rash popular, Rash pruritic, Solar dermatitis, Solar urticarial, Sunburn, Erythema, Dry skin),
 - all and related gastrointestinal (GI) perforation (MedDRA SMQ: Gastrointestinal perforation, ulceration, haemorrhage or obstruction: sub-category Gastrointestinal perforation),
 - all and related TEAEs leading to death,
 - all and related TEAEs leading to treatment discontinuation,
 - all and related TEAE resulting in hospitalization or prolonged hospitalization.
- . For related TEAEs the relationship to pirfenidone, nintedanib or both investigational drugs will be assessed.

The number and percentage of patients with CTCAE grade 3-4 laboratory liver test results will also be included in this overview.

If relationship to study drug is missing, the event will be presented in the 'All TEAEs' column. A listing presenting all AEs with missing relationship will be added.

The following categories of TEAEs as presented in the overview will be summarized by system organ class (SOC) and preferred term (PT):

- all and related treatment-emergent adverse events (TEAE),
- all serious treatment-emergent adverse events (serious TEAE),
- all non-serious treatment-emergent adverse events (non-serious TEAE),
- all severe (Grade 3 – 5) treatment-emergent adverse events (severe TEAE),
- all TEAEs resulting in hospitalization or prolonged hospitalization

Similar summary presentations will be provided for patients with TEAEs leading to dose modification.

Frequencies and percentages of patients experiencing (at least) one event in the respective category will be presented by decreasing frequencies. If patients have more than one AE within a SOC or PT they will be counted only once for the respective SOC or PT. Total numbers of TEAEs will be provided for each SOC and overall.

Special interest in this study will be on assessment of treatment discontinuation. Therefore, TEAEs leading to treatment discontinuation will be summarized for TEAEs leading to discontinuation of any drug, and for TEAEs leading to discontinuation of both treatments, to pirfenidone alone or to nintedanib alone. Additional presentations for the following categories of TEAEs leading to treatment discontinuation will be presented:

- Serious TEAEs).
- GI event,
- Photosensitivity reaction or rash
- TEAEs by intensity.

All TEAEs indicating "Action taken with pirfenidone/nintedanib due to SAE/AE" = "Drug withdrawn" in the eCRF will be included in these summaries.

Numbers and frequencies of patients with TEAEs by most extreme CTCAE Grade will be provided for any TEAEs and for each SOC and PT. In case the most extreme intensity is missing, it will be replaced by the initial intensity. If both most extreme and initial intensity are missing, AE will be included in the summaries for grade 3 to 5 AEs (i.e. in the total column) and a column for "missing" will be added.

The timing of TEAEs will be assessed by presenting numbers of patients with TEAEs occurring in the first 28 days (Days 0 – 28), from Day 29 to Day 84 (Weeks >4 - 12), and for the total study period by SOC and PT.

Further, Kaplan-Meier curves for time to onset of first adverse event of the most relevant related TEAEs will be provided. These will include the following PTs or baskets (as defined above): Nausea, Diarrhoea, GI disorder basket, Weight decreased, Fatigue, Decreased appetite, photosensitivity or rash basket.

All adverse event data will be listed by patient number and study day of onset. Separate listings will be provided for TEAEs leading to treatment discontinuation, serious TEAEs (STEAEs), adverse events of special interest (AESIs), TEAEs leading to dose modification, TEAEs leading to hospitalization, severe (Grade 3 – 5) TEAEs and deaths.

Non-treatment-emergent AEs (i.e. AEs that start prior to first administration of combination treatment and do not worsen at/after combination treatment, or AEs that start more than 28 days after last dose of combination treatment) will be listed separately.

The following additional analyses will be performed for the purpose of fulfilling the Clinical Trial Registry (CTR) requirements:

- Both Serious Adverse Events and ‘Other’ Adverse Events will be summarized by MedDRA preferred term.

An adverse event is considered ‘Serious’ whether or not it is a TEAE. An adverse event is considered in the ‘Other’ category if it is both, a TEAE and is not serious.

For each Serious AE and ‘Other’ AE, and for each term the following are provided:

- The number of subjects at risk of an event;
- The number of subjects who experienced each event term;
- The number of events experienced.

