4.7.3 Adverse Events	Updated definition for major adverse cardiac event (MACE): Specific terms from SMQs Arrhythmia related investigations, signs and symptoms, Cardiac arrhythmia terms (incl bradyarrhythmias and tachyarrhythmias), Cardiac arrhythmias, Cardiac failure: Cardiac arrest, Cardiac death, Cardio-respiratory arrest, Sudden cardiac death, Sudden death, Ventricular asystole, Agonal rhythm, Sinus arrest, Pulseless electrical	Need to specify terms.

	activity, Torsade de pointes, Ventricular fibrillation, Ventricular flutter, Ventricular tachycardia, Cardiac fibrillation, Cardiac flutter	
	Retching and Somnolence were deleted from the basket for photosensitivity reaction or rash	Terms also belong to other AE baskets
	'All and related elevated liver test results leading to treatment discontinuation' was deleted from the safety summary output.	The link between liver test results and respective AEs not established.
	'Number of events' was removed from the safety overview table.	Numbers of events are presented with the 'by SOC and PT' outputs
	Categories of TEAEs that are presented separately by SOC and PT specified in detail.	Description was not specific.
	Categories of TEAEs leading to treatment discontinuation specified in detail.	Description was not specific
	Analysis of timing of TEAEs added.	Not included in previous version.
4.7.6 Laboratory data	Paragraph added describing grading of laboratory values as per NCI CTCAE, when criteria for grading conflict with normal ranges as per central laboratory. Safety assessment of creatinine values changed from NCI-CTC grading to non-NCI-CTC grading.	Not included in previous version.
4.7.6 Laboratory data	Paragraph added on handling of values below the limit of quantification	Not included in previous version.
4.7.9 Previous and Concomitant medication	Note added that previously administered Pirfenidone will be presented separately.	Presented with previous/concomitant medications, previously.
4.8 Missing Data	Description added for imputation of missing start dates for previously administered Pirfenidone.	Presented with previous/concomitant medications, previously.
Appendix 5 Calculation of GAP Index Categories	Description of derivation of GAP Index added.	Not included in previous version.

TABLE OF CONTENTS

SIGNATURE PAGE.....	2
STATISTICAL ANALYSIS PLAN AMENDMENT RATIONALE.....	3
1. BACKGROUND	11
2. STUDY DESIGN	11
2.1 Protocol Synopsis.....	12
2.2 Outcome Measures	12
2.2.1 Primary Efficacy Outcome Measures	12

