Abbreviation	Definition
%FVC	Percent predicted forced vital capacity
ACS	Acute coronary syndrome
AE	Adverse event
AEGT	Standard Adverse Event Group Terms
ALT	Alanine aminotransferase
AST	Aspartate aminotransferase
BCE	Biostatistical Computing Environment
BID	Twice daily
BMI	Body mass index
BP	Blood pressure
CI	Confidence interval
CTCAE	Common Terminology Criteria for Adverse Events
d	Day
DLco	Carbon monoxide diffusing capacity
ECG	Electrocardiogram
eCRF	Electronic Case Report Form
EOT	End of Treatment
FVC	Forced vital capacity
GCP	Good clinical practice
GI	Gastrointestinal
HR	Heart rate
ICF	Informed consent form
ICH	International Conference on Harmonisation
iDMC	Independent Data Monitoring Committee
IPF	Idiopathic pulmonary fibrosis
IRB	Institutional Review Board
██████	████████████████████ ██████████
LPLV	Last patient, last visit
MACE	Major Adverse Cardiac Event
MedDRA	Medical Dictionary for Regulatory Activities
ms	Millisecond
PDMS	Protocol Deviation Management System
PRO	Patient-reported outcome
QD	Once daily

**Pirfenidone and nintedanib — F. Hoffmann-La Roche Ltd
Statistical Analysis Plan MA29895, Version 2.0, final, 17 May 2017**

QTcF	QT interval corrected using Fridericia's formula
SAE	Serious adverse event
TEAE	Treatment-emergent adverse event
TESAE	Treatment-emergent serious adverse event
TID	Three times daily
TMS	Trial Management System
UA	Unstable angina
ULN	Upper limit of normal
WHO	World Health Organization

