AEs will be coded to a preferred term and system organ class using the Medical Dictionary for Regulatory Activities (MedDRA). Laboratory abnormalities will be graded using the Common Terminology Criteria for Adverse Events (CTCAE). Prior and concomitant medications will be coded using the World Health Organization (WHO) Drug Dictionary.

Because this is a safety and tolerability study that is not designed to assess efficacy, no formal statistical hypotheses for efficacy will be assessed. The efficacy analyses will be limited to descriptive statistics.

Data summaries will be provided for baseline characteristics; patient disposition; extent of exposure; the number and proportion of patients who complete 24 weeks on pirfenidone at a dose of 1602–2403 mg/d and nintedanib at a dose of 200–300 mg/d (with 95% confidence interval [CI]); the numbers and proportions of patients with a dose reduction or a dose interruption; the number and proportion of patients who discontinued combination treatment because of a AE (with 95% CI); the total number of days on combination treatment at an pirfenidone dose of 1602–2403 mg/d and a nintedanib dose of 200–300 mg/d; the total number of days from the start of combination treatment to discontinuation of one or both study treatments; the final prescribed doses of pirfenidone and nintedanib; and the reasons for premature discontinuation of combination treatment.

AEs and SAEs leading to discontinuation will be summarized by incidence, severity, seriousness, and relationship to treatment. Additional summaries will be provided for the numbers and proportions of patients with a Major Adverse Cardiac Event (MACE), a cerebrovascular event, a bleeding event, or a thromboembolic event; the numbers and proportions of patients discontinuing combination treatment for a liver test abnormality, a GI event, or a photosensitivity reaction/rash; the numbers and proportions of patients with an emergency department visit or hospitalization; and deaths.

Observed and change values for clinical laboratory and vital signs data will be summarized. Grade 3 and 4 laboratory abnormalities will be summarized by CTCAE grade, and shift tables by CTCAE grade will be provided.

**Pirfenidone and nintedanib — F. Hoffmann-La Roche Ltd
Statistical Analysis Plan MA29895, Version 2.0, final, 17 May 2017**

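### SAP V2.0 defines MACE by 15 arrest, death and arrhythmia terms with no infarction or acute coronary syndrome term, so the count does not match its name

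*SAP*

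**What the plan says.** All references are to SAP V2.0 (17 May 2017) unless stated.

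- **Section 4.7.3, safety overview.** The MACE row is introduced as "all and related major adverse cardiac event (MACE), (Specific terms from SMQs Arrhythmia related investigations, Signs and symptoms, Cardiac arrhythmia terms". After the remaining SMQ names comes an enumeration that ends "Torsade de pointes, Ventricular fibrillation, Ventricular flutter, Ventricular tachycardia, Cardiac fibrillation, Cardiac flutter", where the bracket closes. Nothing marks the list as giving examples only.
- **Same overview, separate row:** "all and related ischemic heart disease (MedDRA SMQ: Ischemic heart disease". A further vascular-event row gives angina, infarction, transient ischaemic attack and stroke as its examples and is built from four SMQs, including Ischemic heart disease.
- **Amendment rationale.** The MACE change is itemised with every term. The reason given is "Need to specify terms", and no change of scope is mentioned.
- **List of Abbreviations.** "Acute coronary syndrome" (ACS) and "Unstable angina" (UA) are still defined, although no visible V2.0 text uses either.
- **Appendix 1 synopsis, Statistical Methods.** It promises "numbers and proportions of patients with a Major Adverse Cardiac Event (MACE), a cerebrovascular event, a bleeding event, or a thromboembolic event". It does not list the components of MACE.
- **Section 4.7.3, tables by preferred term.** These are introduced by "The following categories of TEAEs as presented in the overview will be summarized by system organ class (SOC) and preferred term (PT". All treatment-emergent events are among the categories; MACE is not.

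**The concern.** The row is called a major adverse cardiac event row, yet its content is arrest, sudden or cardiac death, and rhythm disturbance. Infarction and unstable coronary disease cannot enter it. The study's stated objective is the safety and tolerability of the combination, and the overview is where a reader looks first. A low or zero MACE figure would be read as covering infarction, which it does not. Conversely, a single ventricular tachycardia record of any grade would be reported as MACE.

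**Working it through.** The plan gives no MACE figure to reproduce, so the check is a count of terms, a comparison of passages and one division.

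**Step 1: classify the listed terms (section 4.7.3).**

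| Group | Terms | Number |
|---|---|---|
| Death | cardiac death; sudden death; sudden cardiac death | 3 |
| Arrest or absent output | cardiac, cardio-respiratory and sinus arrest; ventricular asystole; pulseless electrical activity; agonal rhythm | 6 |
| Other arrhythmia | ventricular tachycardia, fibrillation and flutter; cardiac fibrillation and flutter; torsade de pointes | 6 |
| Infarction, ACS or unstable angina | none | 0 |

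Total 3 + 6 + 6 = 15, all distinct. A text search of the list for infarct, angina, coronary and ischaemic (both spellings) gives 0 hits each.

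**Step 2: check the source SMQs.** Read as in the amendment rationale, where the arrhythmia-related investigations, signs and symptoms form one name, there are four: that one, two cardiac arrhythmia queries, and cardiac failure. Ischemic heart disease is 0 of 4, although the same overview uses that SMQ in two other rows.

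**Step 3: apply the definition.**

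| Patient | MACE row | Where else the event appears |
|---|---|---|
| Non-fatal infarction, no listed term | 0 | Ischaemic heart disease row, vascular-event row, table of all treatment-emergent events, listings |
| Ventricular tachycardia of any grade | 1 | Table of all treatment-emergent events, listings |

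**Step 4: can the overview rows be combined instead?** Not reliably. The ischaemic row is a whole SMQ, wider than infarction plus ACS/unstable angina. The vascular-event row also takes in haemorrhages and emboli. Overview rows count patients, so adding two rows counts a patient with events in both twice.

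**Step 5: size.** With the planned 80 patients, one patient is 1/80 = 1.25 percentage points. Any number k of patients with infarction or ACS but no listed term contributes 0 to the row instead of k × 1.25 points. The plan gives no expected rate for these events, so k is left open.

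**The case against.** The strongest defence has four parts.

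1. *Nothing is hidden.* Infarctions are counted in the ischaemic heart disease and vascular-event rows, shown by preferred term in the table of all treatment-emergent events, and listed by patient. This is correct. A reader might infer that infarctions drop out of the safety report, or that no planned table shows which terms occurred; section 4.7.3 supports neither. It limits the consequence but does not correct a row with the wrong name.
2. *There is no strict contradiction.* The synopsis promises MACE without components, and section 4.7.3 supplies a definition and a count. SAP V1.0 did list infarction and ACS/unstable angina, but it is superseded, and a difference between versions is not an error. That stands, and the point does not rest on V1.0. It rests on a V2.0 row whose name and content disagree, after a change described only as specifying terms.
3. *Leftover abbreviations prove little.* Agreed: they are weak support, and the conclusion would hold without them.
4. *The row is descriptive.* There are no hypothesis tests and no interval is planned for this row. That is why the matter is the meaning of a reported safety figure and not any inference.

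A reader might also infer that the plan needs a cardiovascular cause-of-death rule and a decision on stroke. The documents do not show that either is required, and the defect can be removed without them.

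**Conclusion.** The point holds as a mismatch between label and content. The MACE row has 0 of 15 terms for infarction or ACS/unstable angina and draws on 0 of 4 SMQs for ischaemic heart disease, so the number reported as MACE would not respond to those events and would respond to any ventricular tachycardia. It should be corrected because it changes a reported safety figure in a safety study. It does not touch the primary outcome or the named secondary outcomes.

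Two assumptions are made: the list is programmed literally, as its closed form invites, and the denominator is about 80.

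A minor, separate note concerns the liver. The synopsis promises counts of patients discontinuing for three reasons: a liver test abnormality, a GI event, or photosensitivity/rash. Section 4.7.3 has discontinuation categories for the last two only. A reader might infer a silent omission of hepatic discontinuations. That is not so: the amendment rationale discloses removal of the liver-test row because laboratory results could not be linked to adverse events, and the cases remain in the planned listing of events leading to discontinuation. What is left is two passages that need reconciling.

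**What to change.** 1. Add to the MACE definition the myocardial infarction and ACS/unstable angina preferred terms from the Ischemic heart disease SMQ.
2. Show the present 15 terms as a row of their own under a descriptive name, such as cardiac arrest/sudden death/serious arrhythmia.
3. Footnote the term list of both rows in the overview table.
4. If the sponsor prefers not to widen MACE, rename the present row. This is the minimum that removes the mismatch.

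The cost is a short term list, one extra table row and two footnotes. The adverse event terms are already collected.

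For the liver note, either state in section 4.7.3 that the synopsis count will not be produced, or add a patient count of Appendix 4 terms with the action taken recorded as drug withdrawn. Label that count as a proxy based on adverse events, because Appendix 4 also contains diagnoses and prothrombin-time terms and is not a pure liver-test list.

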2.2.5 Safety Outcome Measures

The primary safety outcome measure is:

- Proportion of patients who complete 24 weeks of combination treatment on pirfenidone at a dose of 1602–2403 mg/d and nintedanib at a dose of 200–300 mg/d.

Secondary safety outcome measures are:

- Proportion of patients who discontinue pirfenidone, nintedanib, or both study treatments because of adverse events before the Week 24 visit,
- Total number of patient days of combination treatment with pirfenidone at a dose of 1602–2403 mg/d and nintedanib at a dose of 200–300 mg/d,
- Total number of days from the initiation of combination treatment to discontinuation of pirfenidone, nintedanib, or both study treatments,
- Frequency and timing of Adverse Events (AEs) and Serious Adverse Events (SAEs).

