4.8 MISSING DATA

In general, missing data will not be imputed. Exceptions will be made for the data related to adverse events and concomitant medications as described below.

For adverse events, missing start or end dates will only be imputed for determination of whether the adverse event is considered to be treatment-emergent or not by using the following principles:

Incomplete or missing onset dates will be imputed to the earliest date possible (using any reliable portions of the onset date that are available and the eCFR flag on whether the event/medication occurred prior to study drug administration) following the first dose of combination treatment. Note that the onset day is considered unreliable if the month or year portions of the date are missing, and the onset month is considered unreliable if the year portion of the date is missing. If, given the completed portions of the adverse event onset date and the known first combination treatment start date, the event could not have started after the first dose of combination treatment, then the adverse event will be considered non-treatment-emergent and the onset date will be left as an incomplete date.

If the stop date is completely missing, then the event will be assumed to be ongoing and a stop date will not be imputed.

For imputation and handling of missing intensity or relationship to study medication, please see Section [4.7.3](#).

All other missing or incomplete adverse event data will be left as missing.

For concomitant medications, missing start or end dates will only be imputed for determination of whether the concomitant medication is considered to be prior, on-treatment, post-treatment. The eCRF flag 'Select if (medication) taken prior to study' will be used in addition.

For previous pirfenidone treatment, recorded in the concomitant medication eCRF, missing month and day for the start year will be imputed with July 1st of the respective year. If the day is unknown, the 15th of the respective month will be imputed. Imputations will only be used for calculation of duration of previous pirfenidone treatment. An imputation will only be applied if not artificially leading to a previous treatment period of more than 16 weeks.

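### TEAEs with missing causality are left out of the 'related' counts, so related-event proportions can be understated; the related-event Kaplan-Meier curves and one-drug assessments have no rule (minor)

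*SAP*

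**What the plan says.** The rule is in SAP V2.0, section 4.7.3: "If relationship to study drug is missing, the event will be presented in the 'All TEAEs' column". The next sentence adds: "A listing presenting all AEs with missing relationship will be added". Section 4.8 sends the reader back to 4.7.3, with the words "For imputation and handling of missing intensity or relationship to study medication", and otherwise holds that "In general, missing data will not be imputed". No other rule for missing causality exists in the SAP.

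Relatedness is used in three places in 4.7.3:

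- The safety overview, where nearly every category is shown for all and for related events, with relationship assessed for pirfenidone, nintedanib or both.
- The tables by system organ class and preferred term, where only the first category is split: "all and related treatment-emergent adverse events (TEAE").
- The onset curves: "Kaplan-Meier curves for time to onset of first adverse event of the most relevant related TEAEs will be provided". These cover seven terms or baskets, among them nausea, diarrhoea, decreased appetite and rash.

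For missing intensity the same section says: "If both most extreme and initial intensity are missing, AE will be included in the summaries for grade 3 to 5 AEs". The sentence goes on to specify that this means the total column, and that a separate column for missing values is added.

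**The concern.** Section 4 bases percentages on the total population or the region unless stated otherwise. An event without a causality assessment is therefore out of the related numerator while its patient remains in the denominator. For that row, this gives the same arithmetic as a judgement of not related, although the SAP makes no such judgement.

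The study exists to describe safety and tolerability when nintedanib is added to pirfenidone, and attribution to one drug, the other or both is part of that description. A rule that can move related proportions in only one direction, towards the favourable side, and that leaves no trace in the tables themselves deserves a correction. Two further cases have no rule: the related-event curves, and an event whose relationship is recorded for one drug and blank for the other.

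**Working it through.** The plan attaches no figure to this rule, so there is none to reproduce. The check has two parts.

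**1. The SAP's rules for incomplete adverse event data, side by side (V2.0)**

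| Missing item | Section | Treatment | Visible in the summary table? |
|---|---|---|---|
| Onset date | 4.8 | Set to the earliest possible date after the first combination dose | Leans towards counting the event as treatment-emergent |
| Intensity | 4.7.3 | Initial intensity used; if that is also missing, entered in the grade 3 to 5 summaries through the total column | Yes, by an added missing column |
| Relationship | 4.7.3 | 'All TEAEs' column only | No; a separate listing only |

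Section 4 also allows a category for missing values in categorical summaries where appropriate. Of the three items, relationship is the only one neither assigned conservatively nor shown as missing within a summary.

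**2. Size of the effect**

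Inputs: N = 80, the approximate planned size (section 2.3). The frequency of missing causality is not in the SAP, so the values of k, R and m below are assumptions.

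*Per patient.* One affected patient moves a row by 1/80 = 1.25 percentage points. If r patients are counted as related under the rule and k more have only an unassessed event in that row, the row lies between r/80 and (r + k)/80. Taking r = 40 (50.0%) as an illustration:

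| k | Upper bound (40 + k)/80 |
|---|---|
| 0 | 50.0% |
| 1 | 51.25% |
| 2 | 52.5% |
| 4 | 55.0% |
| 8 | 60.0% |

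*By assumed rate.* Let R be the true proportion of patients with a related event, and m the share of them whose only qualifying event has no causality recorded. The shortfall is R × m:

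| R | m = 1% | m = 5% | m = 10% |
|---|---|---|---|
| 20% | 0.2 points | 1.0 | 2.0 |
| 50% | 0.5 | 2.5 | 5.0 |
| 80% | 0.8 | 4.0 | 8.0 |

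In patients, the extremes are 80 × 0.20 × 0.01 = 0.16 and 80 × 0.80 × 0.10 = 6.4.

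*Uncommon rows.* If five patients truly have a related event and one lacks the assessment, four are shown: a relative undercount of 1/5 = 20%, or 1.25 points. This too is only an illustration.

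**Where the effect is zero.** It is zero if no causality is missing, if the patient already has another event in the same row judged related, or if the unassessed event is truly unrelated. Rows for all TEAEs are never affected.

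**Kaplan-Meier curves.** The SAP is silent. If the program simply selects events recorded as related, a patient whose only such event is unassessed has no event in the curve, and one whose first event is unassessed enters at a later related event. This is inferred from silence, not a stated rule.

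**The case against.** The strongest reply is that the rule is explicit, prespecified and consistent with the general policy of not imputing. A reader might infer that the SAP counts these events as unrelated and so understates the toxicity of the combination. The text does not support that:

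- The SAP never classes the events as unrelated and plans no unrelated row or column. They stay in the 'All TEAEs' column and are listed.
- Overall toxicity is not understated. The tables of serious, non-serious, severe and hospitalization events by organ class are for all TEAEs. Discontinuation summaries by drug select on the action recorded as drug withdrawn. The primary outcome, "Proportion of patients who complete 24 weeks of combination treatment on pirfenidone at a dose of 1602–2403 mg/d and nintedanib at a dose of 200–300" (milligrams per day), does not use causality, and the secondary safety outcomes as worded do not either.
- The contrast with missing intensity is weaker than it first looks. That rule gives the event no grade. It puts it in a total column and flags it as missing, which is partly parallel to the 'All TEAEs' column plus a listing.
- The curves are not the only timing analysis. Section 4.7.3 also tabulates TEAEs by period, regardless of causality.
- The handling of an event blank for one drug is not described, and the eCRF and the protocol sections on causality are not at hand.
- Counting every unassessed event as related brings the opposite bias.

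All of this stands as a limit on the point. What it does not remove is the one-way effect on the related rows and the related table by organ class and preferred term, which a listing does not change. Nor does it supply a rule for the curves or for partial assessments. The opposite bias is met by a footnote with the number assigned, from which a reader can see both bounds.

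**Conclusion.** The point holds in limited form. Under section 4.7.3, TEAEs with missing relationship are absent from the related rows of the overview and from the related table by organ class and preferred term, while their patients remain in the denominator. If any causality is missing, related proportions can be understated by up to 1.25 points per affected patient at N = 80. An actual understatement requires that the event is truly related and that the patient has no other related event in that row. How often this will occur is unknown from the SAP, and it may be never.

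The missing rule for the related-event curves and for events assessed against one drug is a gap in specification, not a demonstrated error. The wider conclusion that toxicity as a whole is understated does not follow, since the all-TEAE, drug-withdrawn and primary analyses are untouched. Severity: minor.

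**What to change.** Replace the rule in 4.7.3 with one along these lines: a TEAE with missing relationship is counted as related to the drug or drugs for which the assessment is missing, in the related rows of the overview, in the related table by organ class and preferred term, and in the Kaplan-Meier curves for related TEAEs. Footnote the number of patients so assigned in each output, so that the count without them is also visible. Keep the planned listing.

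The cost is a sentence in the SAP and a small programming change. Related counts become slightly less favourable and may include some events that are truly unrelated; the footnote shows by how much.
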